5.2 CONSENTING PARTICIPANTS

There is a three-step 'eligibility confirmation and consenting process'

Three-step eligibility confirmation and consenting

TASK team telephones to confirm eligibility & consent, collect baseline data, randomise and commence treatment

Start treatment
www.tasktreatment2.org
or
www.tasktreatment3.org

- TASK researcher phones potential participant, confirms eligibility and consent., countersigns electronic consent form and emails a copy to participant

- 1) Potential participant completes online '*Sign up form*' which comprises of A) Eligibility checklist, B) Informed Consent Form (ICF), and C) Personal details
- 2) TASK research team verifies participant's details and eligibility on the '*Sign up form*' by checking TRAK/Scottish Stroke audit/GP summary sheet
- 3) TASK research team phones potential participant for final verification of identity, eligibility, and confirmed the potential participant has personally provided the electronic signature on the ICF. TASK researcher countersigns the electronic consent form, emails copy to participant

Once 3) is completed, while still on the telephone with the participant the TASK researcher

- completes baseline data collection (including participant's baseline [T0] survey)
- randomizes participant and provides login and password for the allocated treatment website
- schedule the first telephone session for TASK-CBT participants
- provides simple instructions for TASK-CBT and TAS- relax participants to log on to their treatment website

The TASK researcher also

- sends participant an electronic copy of the fully signed informed consent form by email
- sends participant a TASK participant card for the allocated treatment by post

Other considerations

- Interested potential participants are encouraged to read all the information on the PIS (website or paper), and take as much time as they need before completing the '*Sign up form*'
- Paper version of the TASK study ICF is available on request
- Easy-access version of the '*Sign up form*' is available online with text-to-speech function
 - Potential participants with sight impairment should complete this version with assistance from family member/ friend

5.2.1 Withdrawal of Study Participants

Participants are free to withdraw from the study at any point or a participant can be withdrawn by one of the TASK trial investigators. If withdrawal occurs, the primary reason for withdrawal will be documented in the participant's case report form, if possible. The participant will have the option of withdrawal from

- (i) all aspects of the trial but continued use of data collected up to that point
- (ii) all aspects of the trial with removal of all previously collected data.
- (iii) all aspects of the trial with removal of previously collected

"Stopping rules" and "discontinuation criteria"

- Participant loses capacity during the study period

6 STUDY ASSESSMENTS

6.1 STUDY ASSESSMENTS

Who completes the assessment(s)	T0: baseline (before randomization)	T1: at end of intervention (6-10 weeks post randomization)	T2 primary endpoint: (20-30wks post- randomization)	
Participant	Generalized Anxiety Disorder-7 (GAD-7) Fear Questionnaire (FQ) Patient Health Questionnaire-2 (PHQ-2) Modified Rankin Scale (mRS) EuroQol5D5L-Visual Analog Scale (EQ5D5L-VAS)	GAD-7 FQ PHQ-2 mRS EQ5D5L-VAS On medication for mood or anxiety Y/N	GAD-7 FQ PHQ-2 mRS EQ5D5L-VAS On medication for mood or anxiety Y/N	Participant feedback on first intervention
TASK-CBT participant only		Throughout the first intervention (TASK-CBT only): 5 online TASKs--self-completed questions		
TASK researcher	Demographics Date of index event Diagnosis Current psychiatric treatment Past medical history Past psychiatric history			
TASK Therapist	Audio-recording of all 6 telephone-guided sessions	Therapist's manual & record'		
Wearable device (GENEActiv)	Wearable for the entire study period (20- 30 weeks)			

7 DATA COLLECTION

[figure not shown]
- All data collection, including the consent form is carried out online via electronic data collection instruments created in REDCap (Research electronic data capture, hosted by the University <https://redcap.cir.ed.ac.uk/>)
- The detailed security arrangements of REDCap are found in 11.2.7
- Our websites provide web links for participants to click on. Once clicked participants are taken to the relevant redcap web address to complete the questionnaire (see diagrams below).
- All personal data are stored on the REDCap database, hosted by the University of Edinburgh's server (see 11.2.7)
- Other than the participant's email address, no personal data are entered on the websites

The following diagrams demonstrate how all of TASK trial's data are collected from the initial 'sign up':

1) The REDCap 'Sign up form'

Potential participants are interested in taking part in the TASK trial and visits our website www.task4stroke.org

- By clicking on 'Sign up form' button participant is taken to a REDCap's web address hosted by the University of Edinburgh, where participant can enter their details on the 'sign up form'
- All data entered are stored in the REDCap database at University of Edinburgh

Visit www.task4stroke.org to see example of the 'Sign up form'

This form also comes in paper version as the TASK ICF

[figure not shown]
On this REDCap 'sign up form' potential participants provide consent for us to contact them using their personal data which they provide on this form--surname, last name, date of birth, postal address, telephone number.

2) **TASK researcher confirms consent and collect baseline (T0) data over the phone.**

- TASK researcher
 - phones the potential participant who has completed the 'Sign up form'
 - confirms eligibility and consent over the phone
 - countersigns the electronic consent with an electronic signature
 - emails participant a copy of the countersigned consent form
 - collects baseline data from participant over the phone
 - randomizes the participant into one of two treatments
 - provides login instruction and email address to the treatment website
 - makes a telephone appointment (if allocated to the TASK-CBT group)

3) **The 5 online tasks** on the TASK-CBT website (www.tasktreatment2.org)

7.1 Source Data Documentation

- All study data are first captured electronically on REDCap and then printed as a pdf file to be filed as paper Case Report Form (CRF) to be stored in the Investigator Site File (ISF)
- Any additional paper record of participant's data e.g. GP's summary sheet of past medical and drug history is stored with the paper CRF in the ISF

7.2 Case Report Forms

- Electronic CRFs are stored on REDCap database and printed as PDF files to be kept in physical storage in the ISF

8 STATISTICS AND DATA ANALYSIS

8.1 SAMPLE SIZE CALCULATION

- As this is a feasibility RCT designed for process evaluation, we did not calculate sample size
- We aim to recruit around 40 participants in this feasibility trial

8.2 PROPOSED ANALYSES

- Feasibility endpoints as listed in 2.2.1 –these are summarized as proportions (%) and free text
- Descriptive data (mean, standard deviation) from clinical outcomes at T0, T1, T2
 - mRS, EQ5D5L-VAS, GAD-7, PHQ-2, FQ
- Between group differences in clinical outcomes
- Missing answers within each clinical outcome measure is unlikely as values must be provided to complete the electronic survey
- Non-completion—missing answers/ surveys despite all attempts to contact participant for completion is a feasibility outcome in this trial
- Anonymised raw data obtained from the GENEActiv device in the sub-study are sent to data scientist ([name]) at the Usher Institute at University of Edinburgh for analysis

9 ADVERSE EVENTS

- It is possible that participants experience emotional distress, or worsening of their anxiety or mood during the TASK trial
- The TASK therapist is also a stroke physician and geriatrician with experience at delivering CBT in neurology patients. Stroke physicians are experienced in handling emotional sensitive topics and anxiety and will act in accordance with clinical needs of situation this may include postponing call for another day or on other occasions it may be appropriate to slightly prolong call in order to provide the required reassurance

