EQ5D5L-VAS	EuroQol 5D 5L Visual Analogue Scale
FQ	Fear Questionnaire
GAD	Generalized Anxiety Disorder
GAD-7	7-item Generalized Anxiety Disorder Questionnaire
GCP	Good Clinical Practice
ICF	Informed Consent Form
ICH	International Conference on Harmonisation
mRS	Modified Rankin Scale
PI	Principal Investigator
PIS	Participant Information Sheet
QA	Quality Assurance
RCT	Randomized Controlled Trial
REC	Research Ethics Committee
SAE	Serious Adverse Event
SAR	Serious Adverse Reaction
SOP	Standard Operating Procedure
SUSAR	Suspected Unexpected Serious Adverse Reaction
TIA	Transient Ischaemic attack

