1.2 RATIONALE FOR STUDY

Research question

Is it feasible to compare the effectiveness of the telephone-guided web-based TASK-CBT with web-based self-guided TASK-Relax in a web-enabled randomized controlled trial?

Why is this study important to patients, health service and current policies?

Anxiety problems after stroke are common and disabling. There is little research evidence to guide how to treat anxiety after stroke. Access to psychological care after stroke is difficult. We need to deliver an anxiety intervention to large number of stroke and TIA patients, efficiently and economically to ensure its long-term sustainability in the NHS. Our intervention is developed in line with the Scottish Mental Health Strategy for 2017-2027.

Treatment to be tested

We know that cognitive behavioural therapy (CBT) works for anxiety in people who have not had a stroke. Many anxiety issues reported by stroke patients can potentially be targeted by CBT. We developed CBT treatment that are specifically tailored to stroke survivors. Before we can provide TASK-CBT to a large population of stroke survivors, we need to test whether these treatments have any real benefits to patients in a clinical trial setting.

Feasibility of our method to minimize bias in a RCT of psychological intervention

The type of comparator group in an RCT of psychological intervention can influence effect size(6). Rather than using a 'treatment as usual' (TAU) or waitlist control as comparator, we are comparing group receiving TASK-CBT & group receiving TASK-Relax (active comparator).

Establishing any harms of our intervention

It is not clear, but important to establish whether there is any potential harm of a telephone-guided web-based CBT intervention for stroke and TIA patients. We will do that by asking participants to complete a feedback survey at the end of the study period.

Feasibility in conducting a nationwide web-enabled RCT conducted by a single centre

We designed the trial procedures with the view of conducting a large-scale clinical trial that will recruit nationwide from a single centre in the future. We will use the feasibility data from this present study to refine our trial design.

Feasibility of measuring objective outcomes using a wrist-worn wearable device (a substudy)

Wearable device can collect objective physiological and behavioural measures, complementing and potentially replacing self-reported outcomes used in clinical trials of a wide range of interventions in

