2 STUDY OBJECTIVES

2.1 OBJECTIVES

2.1.1 Primary Objectives

Objective 1: Feasibility of web-enabled RCT procedures

Objective 2: Feasibility of TASK-CBT & TASK-Relax interventions

Objective 3: To establish any harm arising from TASK-CBT or TASK-Relax interventions

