10.3 STUDY MONITORING AND AUDIT

As 10.2.

There is no data monitoring committee planned for this study

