12.2 MANAGEMENT OF PROTOCOL NON COMPLIANCE

Protocol deviations will be recorded in a protocol deviation log and logs will be submitted to the sponsors every 3 months. Each protocol violation will be reported to the sponsor within 3 days of becoming aware of the violation. All protocol deviation logs and violation forms should be emailed to [contact]

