12.3 SERIOUS BREACH REQUIREMENTS

If a potential serious breach is identified by the Chief investigator, the co-sponsors ([contact]) must be notified within 24 hours. It is the responsibility of the co-sponsors to assess the impact of the breach on the scientific value of the trial, to determine whether the incident constitutes a serious breach and report to research ethics committees as necessary.

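### The protocol states no procedure for recording, assessing or reporting serious adverse events, although harm is a primary objective

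*Combined protocol and SAP*

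**What the plan says.** Protocol Section 2.1.1 makes harm a primary aim: "Objective 3: To establish any harm arising from TASK-CBT or TASK-Relax interventions". Section 1.2 gives the method: "We will do that by asking participants to complete a feedback survey at the end of the study period". Section 2.2.1 places that survey at T2, 20-30 weeks after randomisation, and takes from it the percentage reporting unwanted effects, the percentage who found the treatment helpful, and free text.

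Section 9 has two bullets. The first is "It is possible that participants experience emotional distress, or worsening of their anxiety or mood during the TASK trial". The second concerns the therapist, a stroke physician, who "will act in accordance with clinical needs of situation this may include postponing call for another day" or, in other cases, extending it a little to reassure.

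The abbreviation list expands SAE, SAR and SUSAR ("Suspected Unexpected Serious Adverse Reaction"), but the body of the protocol does not use these terms.

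Other kinds of incident do have a reporting route. Section 12.2 says "Each protocol violation will be reported to the sponsor within 3 days of becoming aware of the violation". Section 12.3 says that for a potential serious breach the co-sponsors "must be notified within 24 hours". Section 10.3 adds: "There is no data monitoring committee planned for this study".

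**The concern.** A section on adverse events would normally say what counts as serious, where it is written down, who judges its relation to treatment, and who is told by when. Section 9 answers none of these, and no other section does so in its place.

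Two things are at stake. The first is oversight while the trial runs. Section 12.5 allows the investigators or co-sponsors to stop the study for clinical reasons, but the protocol sets up no flow of clinical information on which the co-sponsors could act. The second is what can be concluded under Objective 3. The only planned measurement depends on the participant completing a survey at T2, and those with the gravest events are the least able to do so. A harm summary built on returned surveys alone could look clean for that reason.

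**Working it through.** The question is one of procedure, and the plan has no figure to reproduce. The check sets the provisions side by side and then follows one event through them.

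**Step 1. Reporting routes compared.**

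| Element | Protocol violation (12.2) | Serious breach (12.3) | Serious adverse event (9 and elsewhere) |
|---|---|---|---|
| Record | Log and violation form | Notification to co-sponsors | None designated |
| Assessor | Not stated | Co-sponsors | None named |
| Recipient | Sponsor | Co-sponsors, then ethics committees where needed | None named |
| Time | 3 days | 24 hours | None stated |

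**Step 2. Other places an event could surface.**
- Section 5.2.1: the main reason for withdrawal goes in the case report form where this can be done. Loss of capacity is a discontinuation criterion. No notification is attached to either.
- Section 7, item 4: the team telephones participants whose surveys remain incomplete, to obtain the survey. Nothing says what to record if the call reveals a death or admission.
- Section 1.1: TASK-CBT calls are audio-recorded and documented by the therapist. This applies to one arm only.
- Section 6.1: GAD-7 and PHQ-2 at T0, T1 and T2 could show worsening anxiety or mood, but not an admission or death.
- Section 2.2.1: free text in the T2 survey, from those who return it.

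**Step 3. One event followed through.** Suppose a TASK-Relax participant dies between T1 and T2. The single introductory call is long past. The T2 email and text reminder go unanswered and the team telephones. It may learn of the death then. The death may be entered as a withdrawal reason. If it is not, Section 8.2 treats the missing survey as non-completion, which is a feasibility outcome. No step requires a seriousness or relatedness judgement, or a report to the sponsor or REC.

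**Step 4. Contact by arm (Section 1.1).**
- TASK-CBT: 6 calls of 30-40 minutes, so 6 × 30 = 180 to 6 × 40 = 240 minutes.
- TASK-Relax: 1 call of 20 minutes.
- Ratio of call time: 180/20 = 9 to 240/20 = 12.

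If events are noted only when someone happens to be on the telephone, TASK-CBT will tend to show more of them through detection alone.

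**Step 5. Weight of one event.** With 40 participants (Section 4.1), one person is 1/40 = 2.5% of the sample. If the arms are equal, at 20 each (an assumption, since no allocation ratio is stated), one person is 1/20 = 5% of an arm.

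**The case against.** The strongest reply is that silence in the protocol is not absence in practice. Section 11.1 commits the study to the principles of ICH GCP and to meeting any conditions of approval. Section 10.2 leaves the level of monitoring to a sponsor-side risk review, and Section 10.1 gives the sponsor direct access to all records. A sponsor procedure for serious events may exist outside these documents. This stands as a limit on the point. A reader might infer that the sponsor will not hear of a death, admission or self-harm. The documents support only the narrower statement that the protocol does not require it to be told, and does not cite a procedure that would.

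A reader might also infer that such events have no place at all in the data. That goes too far, because the routes in Step 2 could capture some of them. None is dedicated or systematic, and call records exist for one arm only.

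Third, this is a feasibility trial of 40 people receiving telephone and web treatment, and many serious events after stroke will be unrelated to it. That is fair. It bears on how elaborate the procedure should be, and nothing here asks for a data monitoring committee. It does not remove the need for a record when harm is a primary objective.

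Finally, the 24-hour time for serious breaches serves a different purpose. It shows that the protocol sets reporting times elsewhere, but it does not show what the time for a serious event should be. The unused abbreviations are, on their own, an editorial matter.

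**Conclusion.** The point holds in this form: the protocol gives no definition, designated record, assessor, reporting time or recipient for serious adverse events. Objective 3 rests on a T2 survey that some affected participants cannot return, so their events have no dedicated record and may be counted only as non-completion.

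The documents contain no event rate, so the number of events cannot be estimated and none is claimed. The conclusion does not depend on a rate, because a recording route is needed even if nothing happens. It does rest on the supplied text being complete on this matter. Section 9 is present and runs directly into Section 10, with no sign of redaction.

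This should be corrected. It affects what can be said about harm and leaves the other feasibility outcomes intact.

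**What to change.** In Section 9:
- Define a serious adverse event.
- Add one REDCap form (event, date, arm, seriousness, relatedness) for both arms from randomisation, and name the role that assesses seriousness and relatedness.
- State the reporting time and recipient according to the sponsor's and REC's requirements. If a sponsor procedure already exists, cite it.
- State when collection ends. Sections 12.5 and 12.6 keep website access open for about 10 weeks after the primary endpoint, with no survey scheduled in that time.

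In Sections 2.2.1 and 8.2, list serious events by arm under Objective 3 from sources that are the same in both arms: one identically worded question at T1 and at T2, and the outcome of the existing telephone follow-up of non-completers. Use a TRAK check for non-completers only where consent covers it and the participant has not withdrawn. The protocol describes TRAK for identification, eligibility and an enrolment entry, not for outcomes.

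Record events learned at other contacts too, but flag them by source and keep them out of the comparison between arms, because TASK-CBT has six calls and TASK-Relax one.

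The cost is one form, one question per follow-up and a short amendment. The participant information and consent form may need a small change. Some unrelated events will be logged.

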10 OVERSIGHT ARRANGEMENTS

10.1 INSPECTION OF RECORDS

Investigators and institutions involved in the study will permit trial related monitoring and audits on behalf of the sponsor, REC review, and regulatory inspection(s). In the event of audit or monitoring, the Investigator agrees to allow the representatives of the sponsor direct access to all study records and source documentation. In the event of regulatory inspection, the Investigator agrees to allow inspectors direct access to all study records and source documentation.

10.2 RISK ASSESSMENT

The Research Governance and QA office (University of Edinburgh) will review the study and determine if an independent risk assessment will be performed by an ACCORD Clinical Trials Monitor to decide (a) if monitoring is required and (b) if so, at what level. An independent risk assessment may also be carried out by the ACCORD Quality Assurance Group to determine if an audit should be performed before, during and/or after the study and if so, at what locations and at what frequency

10.3 STUDY MONITORING AND AUDIT

As 10.2.

There is no data monitoring committee planned for this study

11 GOOD CLINICAL PRACTICE

11.1 ETHICAL CONDUCT

The study will be conducted in accordance with the principles of the International Conference on Harmonisation Tripartite Guideline for Good Clinical Practice (ICH GCP).

Before the study can commence, all required approvals will be obtained and any conditions of approvals will be met.

11.2 INVESTIGATOR RESPONSIBILITIES

The Investigator is responsible for the overall conduct of the study at the site and compliance with the protocol and any protocol amendments. In accordance with the principles of ICH GCP, the following areas listed in this section are also the responsibility of the Investigator.

11.2.1 Informed Consent

The Investigator is responsible for ensuring informed consent is obtained before any protocol specific procedures are carried out. The decision of a participant to participate in clinical research is voluntary and should be based on a clear understanding of what is involved.

Participants must receive adequate oral and written information – appropriate PIS (online or paper version) and Informed Consent Form (ICF) (online or paper version) will be provided.

The oral explanation to the participant will be carried out either via video of Chief Investigator on www.task4stroke.org, or in person by the Chief Investigator or qualified delegated person, and covers all the elements specified in the PIS and ICF.

All interested potential participants are encouraged to take time to read through the TASK recruitment website including the electronic PIS before completing the ‘Sign up form’. They are encouraged to contact the TASK research team via telephone or email to clarify understanding.

All interested potential participants can take as much time as they need before completing the ‘Sign up form’

The online recruitment video, our PIS (electronic and paper) and the ICF emphasize that the participant may withdraw their consent to participate at any time without loss of benefits to which they otherwise would be entitled.

The participant will be informed and agree to their medical records being inspected by regulatory authorities and representatives of the sponsor(s).

The TASK investigator countersigns the electronic ICF or paper ICF. The participant will receive a copy of this document electronically to their email and a paper copy is filed in the Investigator Site File (ISF).

